We will follow implementation of the therapy as per the published manual, online videos and available implementation guidelines. In addition, the PI recently attended an 8 hour workshop to develop competence in providing the therapy. We argue that Functional Upper Extremity Training⁷⁷ is not a "targeted" intervention according to our definition. That is, the approach does not specifically target a person-ability level because there will be no guidance from a measurement framework from which to choose appropriate tasks to ameliorate underlying specific deficits.

Specific to Aim 1: Compare the effects of targeted rehabilitation versus *non*-targeted rehabilitation on UE motor function.

Hypothesis: Targeted intervention will result in a greater pre- to post-intervention reduction of UE motor impairment when compared to *non*-targeted intervention.

Rationale: The Rasch-based FMA-UE classification defines levels of UE motor ability by describing UE movement tasks (FMA-UE items) which patients in each level can easily perform, cannot perform (too hard), and are well-matched to ability level. This information is the basis for designing task-practice sessions to specifically target the patient movement abilities. Because treatment is likely to induce changes in these variables, it is reasonable to expect changes in participants' Rasch FMA-UE measure.

Approach: *Dependent Variable:* The dependent variable will be change in UE motor impairment as measured by the percent change in the Rasch FMA-UE occurring from pre- to post-intervention. The Rasch FMA-UE percent change will be calculated as Post minus Pre divided by Pre.

Independent Variables: The independent variable is Group. The independent variable has two levels; targeted-therapy and non-targeted therapy.

Data Analysis: ANOVA will be used to compare the mean values of the Rasch FMA-UE change scores for each targeted vs. non-targeted treatment group across each impairment level (mild, moderate, severe). We will correct for multiple comparisons, therefore, significance for all comparisons will be alpha = 0.05/3 = 0.02.

Specific to Aim 2: Determine critical neuromechanical factors that influence response to targeted or *non*-targeted therapy

Hypothesis: Response to targeted therapy will be associated with recovery of "normal" UE movement and muscle activity patterns.

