Rationale: Very little is known about the neural and biomechanical mechanisms contributing to post-stroke UE motor impairment. Identification of the critical kinematic and neural aspects of reach contributing to changes in UE motor impairment occurring with therapy will permit refinement of existing and development of new interventions specifically targeted at improving these motor control process.

Approach: As described in the procedures above, we will collect kinematic and electromyographic (EMG) data to provide information about motor control strategies (kinematic) neural influences on motor output (EMG) responding to therapy.

Dependent Variable: The dependent variable will be change in UE motor impairment as measured by the percent change in the Rasch FMA-UE occurring from pre- to post-intervention as calculated above.

Independent Variables: We hypothesize that 3 independent variables will explain changes in UE motor impairment expected to occur with rehabilitation. These variables will be measured as the percent change in each variable occurring from pre- to post-intervention (post minus pre divided by pre). The variables were chosen because they are reasonable measures of "normal" movement based on the literature, motor control theory and clinical interpretation. Two kinematic variables (trunk movements, elbow extension range of motion) provide information about the strategy utilized to execute the movement. Trunk movement will be calculated as the cumulative distance a marker placed at T-10 travels during the reach. Voluntary elbow extension is calculated as difference between elbow joint angle at start and the joint angle at touch. One EMG variables (Biceps-Triceps co-

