contraction index) provide information regarding neural influences on motor output. The mean amplitude obtained during 5 sec. resting EMG activity will be used as baseline EMG values. For each trial, "time-to-EMG" is calculated as the difference between muscle onset and movement onset. Muscle onset is defined as a rise in EMG exceeding 4 standard deviations above resting EMG. Muscle offset is defined as a decrease in EMG below this value. Movement onset is defined as the time-point when velocity of the wrist marker exceeded 5% peak velocity. Positive time-to-EMG values indicate anticipatory muscle activation (occurred prior to movement onset); negative time-to-EMG values indicate delayed muscle activation (occurred after movement onset). The EMG activity occurring between onset and offset is defined as burst duration. A co-contraction index variable will be defined as Biceps Burst Duration divided by Triceps Burst Duration so that a value equal to 1 reflects simultaneous activity of the agonist and antagonist.

Data analysis: Two multiple regression models will examine the relationships between the dependent and independent variables. One regression model will include variables from all patients involved in targeted-therapy (i.e., pooled data from across UE impairment levels). The second model will include variables from all patients involved in non-targeted therapy.

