We will first investigate assumptions of normality for all variables via visual inspection of probability plots and statistically verified with the Kolmogorov-Smirnov f test. If the data are not normally distributed, they will be logarithmically transformed. Although we expect that all variables will be associated with the FMA-UE person-measure, we do not expect that a simple linear trend will best describe this relationship. It is likely that the response variables have a different impact on the FMA-UE person-measure according the level of UE motor impairment. Thus it is likely that a polynomial relationship exists between the response variables and the dependent variable. To determine whether a linear or polynomial regression model best fits our data we will first cross-plot each response variable against the dependent variable. Visual inspection of the scatterplot will help to facilitate the appropriate model and identify outliers which may affect the model. Outlier data points beyond 3 standard deviations of the mean value of that variable will be inspected to determine if the data was entered correctly. If not, the data point will be considered an aberrant rating and dropped from analysis. When it is determined that a quadratic trend likely best fits the data, we will transform the variable to its quadratic term via its unstandardized residual to compensate for multicollinearity. We will then apply a general linear model regression procedure to the data using SAS. A forced-entry procedure will be employed in which all variables will be examined for each model. Adjusted R-square values, p-values and 95 percent confidence intervals will be calculated.

We will test significance of the coefficient of determination (adjusted R-square value) for each response variable. The null hypothesis tested is that there is no significant association between each response variable and the dependent variable, meaning that the response variable does not contribute to UE motor ability (FMA-UE person measure). The alternative hypothesis is that the association is significant meaning that the response variable is associated with UE motor ability (FMA-UE person measure). We will reject the null hypothesis if $p < 0.05$ which will lead to the conclusion that the response variable does not contribute to the FMA-UE score at a 0.05 significance level.

Specific to Aim 3: Determine critical predictors of the time-course of response to targeted rehabilitation.

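### Aim 2 pools impairment levels within each arm with no level term, so severity differences can pass for mechanisms of recovery; no between-arm slope comparison is pre-specified

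*Protocol*

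**What the plan says.** The protocol section Specific to Aim 2 sets out two regressions. For the targeted arm: "One regression model will include variables from all patients involved in targeted-therapy (i.e., pooled data from across UE impairment levels"). For the other arm: "The second model will include variables from all patients involved in non-targeted therapy". The predictors are percent changes in trunk movement, elbow extension and the biceps–triceps co-contraction index: "We hypothesize that 3 independent variables will explain changes in UE motor impairment expected to occur with rehabilitation". All are entered: "A forced-entry procedure will be employed in which all variables will be examined for each model". Neither impairment level nor baseline FMA-UE is among them. The outcome is percent change in the Rasch measure, defined under Aim 1: "The Rasch FMA-UE percent change will be calculated as Post minus Pre divided by Pre".

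The same section expects effects to vary with severity: "It is likely that the response variables have a different impact on the FMA-UE person-measure according the level of UE motor impairment". Its response is a curve in the predictor: "Thus it is likely that a polynomial relationship exists between the response variables and the dependent variable". Each predictor is tested at 0.05, with 95% confidence intervals. No contrast of slopes between arms is described.

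Table 4 assigns a different targeted treatment to each impairment level and a single non-targeted treatment to all three. Randomisation is within level. The SAP covers only Aim 1, where it does carry impairment level (nested in treatment). It adds nothing for Aim 2.

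**The concern.** A regression pooled over three groups mixes two things: the link between predictor and outcome among patients of the same severity, which is the mechanism Aim 2 is after, and the link between the group means, which can arise from severity alone. Without a level term the two cannot be told apart.

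The protocol itself gives reasons to expect group means to differ:

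- The TMS rationale says that patients with worse baseline deficits tend to gain less.
- Aim 3 expects each impairment level to follow its own recovery pattern.
- Section 3e reports that elbow range of motion differed between every pair of levels. That is a baseline finding, but baseline is the denominator of the elbow predictor.
- In the targeted arm, trunk restraint is used at two levels and not at the third, and trunk movement is one of the predictors.

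At stake is the stated purpose of Aim 2: a predictor that merely tracks severity could be reported as something to target in refining treatment.

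**Working it through.** **Inputs.** The protocol states no sample size or power for Aim 2, so arm size comes from Aim 1. The pilot figures give d = (2.30 − 1.42)/√((1.00² + 0.45²)/2) = 0.88/0.775 = 1.135 (stated 1.13). A two-sample t test at two-sided 0.05 and 90% power needs 17.5, hence 18 per group, as stated. Three levels give 3 × 18 = 54 per arm. The shifts between levels are assumptions.

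**1. Pooled slope when there is no within-level link.** Let predictor and outcome have SD 1 within each level, no association there, and let both means move by m per level step (−m, 0, +m). The between-level variance and covariance are both 2m²/3, so the pooled correlation is r = (2m²/3)/(1 + 2m²/3). With three predictors, residual df = 54 − 4 = 50. The expected t is about r√50/√(1 − r²), and the rejection rate is about Φ(t − 1.96) plus the small opposite tail.

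| m (SD per step) | r | expected t | approx. rate | simulated, level omitted | simulated, level included |
|---|---|---|---|---|---|
| 0.25 | 0.040 | 0.28 | 6% | 5–6% | about 5% |
| 0.5 | 0.143 | 1.02 | 17% | 17–18% | about 5% |
| 0.75 | 0.273 | 2.00 | 52% | 52–54% | about 5% |
| 1.0 | 0.400 | 3.09 | 87% | 88–89% | about 5% |

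The simulated ranges span independent runs with 52 to 54 patients per arm.

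**2. Sensitivity to the assumptions.** With 0.5 SD per step in the predictor and 0.25 SD in the outcome, the rate was 8%. With the outcome highest in the moderate level, it stayed at 4–5% even at 1 SD.

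**3. Does the polynomial step help?** Adding a quadratic term left the rate at 14–17% for m = 0.5 and 80–87% for m = 1.0. The lower figures test the linear and quadratic terms jointly. An effect that differs by level is a predictor-by-level interaction; a curve in the predictor does not represent it and does not remove differences in level means.

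**4. The outcome scale.** Dividing by Pre makes the outcome depend on severity by construction. A 0.5-logit gain is 0.5/(−1.0) = −50% at Pre = −1.0, 0.5/0.1 = +500% at Pre = 0.1, and 0.5/2.44 = +20% at Pre = 2.44. Every severe patient under Table 4 (below −0.22 logits) has a negative denominator. This adds to the worry about pooling, but it also means that the normal, unit-SD outcome in step 1 is only an illustration.

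**5. Can the arms be compared?** In a test data set, two separate fits and one fully interacted model gave the same slope difference (0.49985 in both), with standard errors 0.2242 and 0.2235. A comparison can therefore be formed. Its precision is low: with 54 per arm and standardised variables, SE ≈ √(2/49) = 0.202. Power for a slope difference of 0.3, 0.4 or 0.5 is then 32%, 51% or 70%, and 80% power needs about 0.57. Comparing significance instead would mislead. With equal true slopes of 0.2, 0.3 or 0.4, power per arm is 29%, 56% or 80%, and exactly one arm is significant with probability 2p(1 − p) = 41%, 49% or 32%.

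**6. Which joint model is enough?** When level means shift only in the targeted arm, a joint model with one common level effect still gave false-positive rates of 8–9%, 22% and 49–50% for the targeted slope at 0.5, 0.75 and 1.0 SD. Adding arm-by-level terms brought this to about 5%.

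**The case against.** A reader might infer that the two arms cannot be compared at all. The documents do not support that. Separate models already let every slope differ by arm, confidence intervals are planned, and randomisation within level balances severity between arms. The Aim 2 hypothesis concerns response to targeted therapy and states no between-arm contrast, and the background calls the neuromechanical work exploratory. Nor does the plan say that significance in one arm only would be read as specific to targeting. What stands is that the aim's title covers both therapies, two parallel models invite comparison, and no method for one is written down.

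A reader might also infer that treatment type is a confounder in both arms. It is not: the non-targeted arm receives one treatment at every level. Stratified randomisation does not answer the severity point, however, because it balances the arms and does not protect associations within an arm.

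The strongest objection is to the size. No document gives level differences in percent change, the inflation needs predictor and outcome to shift together, and at 0.25 SD there is almost none. That is correct, so the rates are conditional and the harm is possible, not certain.

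**Conclusion.** The concern holds in this form: Aim 2 omits impairment level from both pooled regressions, so severity differences can appear as individual-level mechanisms, and the polynomial step neither models the expected effect modification nor removes the confounding. The false-positive rate runs from about 5–6% at 0.25 SD per level step to 88–89% at 1.0 SD, assuming equal, same-direction shifts in predictor and outcome, normal data and no within-level association. Smaller or non-monotone shifts do little harm. In the targeted arm a level term adjusts for severity and treatment type together; no analysis of these data can separate them there. That the arms cannot be compared does not follow: the comparison is simply not pre-specified and would be imprecise. For a mechanistic aim this should be corrected, but it does not touch the primary comparison.

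**What to change.** - Add impairment level, as two indicator terms, to each of the two planned per-arm models. Equivalently, fit one model with the three predictors, arm, level, arm-by-level and arm-by-predictor terms. The parameter count is the same: 2 × (1 + 3 + 2) = 12 and 1 + 3 + 1 + 2 + 2 + 3 = 12. A level effect common to both arms is not enough.
- Replace the polynomial step by predictor-by-level terms, only for predictors named in advance, labelled exploratory and as the sample allows. Three predictors by three levels would add six parameters.
- If the arms are to be compared, report the slope difference with its 95% confidence interval, do not compare significance between arms, and say that precision is low.
- State that severity and targeted treatment type cannot be separated.
- Write Aim 2 into the SAP, which is now silent on it.

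The cost is two degrees of freedom in each per-arm model (50 to 48 residual with 54 patients), four in the joint model, and some SAP wording. Level is the stratification factor and is already recorded, so no new data are needed.

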One purpose of the present proposal is to explore the neuromechanical mechanisms contributing to post-stroke UE recovery. There is evidence supporting the hypothesis that several neuromechanical (i.e., kinematic and electromyographic (EMG)) factors are key to recovery. Individuals with stroke demonstrate reduced voluntary elbow extension range of motion⁵² which may be at least partially explained by abnormal elbow muscle co-activity between biceps and triceps.⁵³ Together, these impairments contribute to reduced ability make smooth reaching movements throughout the workspace.⁵⁴ Given this limitation, people with stroke recruit the trunk as an extra degree of freedom.⁵⁴ Anterior trunk flexion is used in place of elbow extension for reaching movements. UE motor recovery is characterized by improved elbow extension,⁵⁵ reduced anterior trunk motion,⁵⁶ and reduced muscle co-activity.⁵⁷

Here we aim to investigate the influence of neuromechanical mechanisms contributing to the treatment related changes in participants' Rasch FMA-UE person ability measure. By investigating the relationship of neuromechanical factors to a person's FMA-UE measure, we will learn more about what neuromechanical factors or mechanisms underlie a person's location within this classification system. As noted in the brief literature review above, several studies relate neuromechanical factors to UE recovery. But in these studies, UE recovery is defined in terms of performance of a single task (e.g., reach-to-point) or in terms of a patient's aggregate score on an assessment. Here, our measurement framework enables us to investigate how neuromechanical factors influence re-acquisition of the underlying construct "UE motor ability" which is defined in terms of specific FMA-UE items that a patient could/could not perform prior to rehabilitation but gained the ability to perform after rehabilitation.

2g. The time-course of UE recovery

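### Aim 2 checks the raw variables for normality instead of the model residuals, and prescribes a log transform that cannot be applied to percent changes that may be negative

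*Protocol*

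**What the plan says.** Protocol section D, Specific to Aim 2, Data analysis, opens with the distributional check: "We will first investigate assumptions of normality for all variables via visual inspection of probability plots", backed by a Kolmogorov-Smirnov test. The remedy follows: "If the data are not normally distributed, they will be logarithmically transformed". No offset, ratio or alternative is given. Residuals appear only in the construction of a quadratic term, and no residual diagnostic is planned.

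The scale of the data is fixed nearby. For the outcome: "The dependent variable will be change in UE motor impairment as measured by the percent change in the Rasch FMA-UE occurring from pre- to post-intervention", with the formula under Aim 1: "The Rasch FMA-UE percent change will be calculated as Post minus Pre divided by Pre". For trunk movement, elbow extension and the co-contraction index: "These variables will be measured as the percent change in each variable occurring from pre- to post-intervention (post minus pre divided by pre".

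The same Data analysis section has values beyond 3 standard deviations inspected for entry errors. If the entry was wrong, "the data point will be considered an aberrant rating and dropped from analysis". No correction step is described.

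The SAP's analysis section covers Aim 1 only and does not change any of this.

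**The concern.** There are two faults in one rule. First, the check is aimed at the wrong quantity. Predictors in a linear regression may have any distribution, and the outcome need not be normal marginally. The assumption concerns the residuals of the fitted model.

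Second, the remedy does not fit the scale. The protocol's background (section B, 2f) describes recovery as including "reduced anterior trunk motion", so improvement on the trunk variable is a negative percent change. The FMA-UE measure is in logits, which may be negative, and a gain divided by a negative baseline is also negative.

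An analyst who reaches this step must either lose those values or invent a workaround after seeing the data. The loss would not be random: whether a value can be logged depends on whether, and from which baseline, the patient changed. That is what Aim 2 studies.

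**Working it through.** The plan states no figure for this step, so the check applies its own formula to values on its own scales.

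**Inputs.** Percent change = (post − pre)/pre (Aims 1 and 2). Severe stratum: baseline below −0.22 logits (Table 4) or below −0.12 logits (section C, text to Table 3). Moderate stratum in Table 4: −0.22 to 2.44 logits. Planned evaluable patients: 18 in each of 6 groups (section D, sample size). Each model pools the three impairment levels of one treatment arm.

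**Sign of the values (illustrative patients).**
- FMA-UE from −1.0 to −0.5, improved: 0.5/(−1.0) = −50%; no logarithm.
- FMA-UE from −0.22 to 0.50, improved: 0.72/(−0.22) = −327%; no logarithm.
- FMA-UE from 0.90 to 2.30 (the pilot targeted means): 1.40/0.90 = +156%; can be logged.
- Trunk path from 200 to 150, improved: −50/200 = −25%; no logarithm.

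**Direction of the loss under a literal log.**
- Trunk movement: patients who improve are lost.
- FMA-UE with a negative baseline: patients who improve are lost.
- FMA-UE with a positive baseline (mild and most moderate patients): patients who do not improve are lost.
- Elbow extension: with a positive baseline excursion, patients who do not improve are lost.

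**Share of patients concerned.** Each model has 3 × 18 = 54 planned evaluable patients, of whom 18 are severe: 18/54 = 33%. Both cuts are negative, so every improving severe patient has a negative value under either. Moderate patients with a baseline below 0 add to this.

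**Scenarios.** The documents give no distribution of baselines or changes across the strata, so the following rests on assumptions.
- FMA-UE, with equal strata and uniform baselines of −3 to −0.22, −0.22 to 2.44 and 2.44 to 4. The share with a negative baseline is 1/3 + (1/3)(0.22/2.66) = 36%, which is also the share of improvers with a negative value. With mean gains of 0.53 to 1.40 (the two pilot gains, 1.42 − 0.89 and 2.30 − 0.90) and SD 0.3 to 1.0, 36% to 44% of all values are zero or below.
- Trunk, with a mean change of −10% to −30% and SD of 20 to 30 points. The share at or below zero runs from Φ(0.10/0.30) = 63% to Φ(0.30/0.20) = 93%.

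**Would an offset rescue the rule?** Adding 1 turns the percent change into post/pre. For trunk distance this is positive, and ln(150/200) = −0.288 is well defined. For FMA-UE it fails: from −0.5 to 0.2 the ratio is −0.4, with no logarithm, and from −1.0 to −0.5 it is 0.5, so an improvement gets a negative log. Elbow extension is a difference of two angles, so its ratio is not guaranteed to be positive either.

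**Outlier rule.** Source exists: the FMA-UE is videotaped, kinematic and EMG signals are recorded, and hard copies are kept. One patient is 1/54 = 1.9% of a model.

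**The case against.** The log step is conditional, and the text neither prescribes nor forbids an offset or ratio. This stands: what is shown is that the rule cannot be executed as written, and deletion is only one consequence. The trigger is plausible, because the moderate stratum spans zero and near-zero denominators give heavy tails, but its frequency is not documented.

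A reader might infer that the rule removes exactly the patients who improve. The documents do not support that. For elbow extension and for positive FMA-UE baselines, the log would lose those who do not improve. Nor is every fall in the co-contraction index a gain. Section B lists "and reduced muscle co-activity" as recovery, but Aim 2 defines the index as a ratio of burst durations in which 1 means simultaneous activity.

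A reader might also infer that whole patients are lost. The protocol drops data points; loss of the patient assumes complete-case fitting. The SAP does provide multiple imputation under missing at random, but that paragraph is framed around missed visits and dropout after Aim 1, and its reach to Aim 2 is unclear. It would not help here in any case. A value made missing by its own sign is not missing at random, and imputing on the log scale would return a positive change for a patient whose change was negative.

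Finally, one might size the outlier rule from the normal tail: 0.0027 × 4 variables × 54 patients = 0.6. Those are valid extremes, which the rule keeps. No entry-error rate is given.

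**Conclusion.** The point holds in a limited form. The normality check is aimed at the variables when it should be aimed at the residuals, and the log remedy cannot be carried out on signed percent changes. Any loss is selective, in a direction that depends on variable and stratum. The firm number is the planned 18 of 54 severe patients per model, for whom any FMA-UE improvement gives a value with no logarithm. The 36% to 44% and 63% to 93% ranges are illustrations under assumed distributions. Actual loss of patients further assumes that the rule is triggered, that the log is applied literally, and that the model is fitted to complete cases.

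The Specific Aims section calls the outcome a change score. On that scale values of zero or below remain possible and the predictors are still percent changes, so the conclusion does not depend on which definition is used. Nor does it depend on which severe/moderate cut applies, though −0.12 and −0.22 must be reconciled.

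This is a low-priority correction: the rule stands under Aim 2, which is not the primary comparison. The outlier part is minor, and the number of values affected is unknown and may be zero.

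**What to change.** Replace the normality and log rule with wording such as: *The residuals of each fitted model will be examined. If they are clearly non-normal or heteroscedastic, robust standard errors or a bootstrap will be used; percent changes will not be log-transformed.* A log ratio, ln(post/pre), may be offered only for predictors that are strictly positive, such as trunk distance.

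Replace the outlier consequence with: *A value found to be entered incorrectly will be corrected from the video, raw signal or hard copy, and set to missing only if no source exists.*

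These changes do not cure the FMA-UE percent change itself. With a negative or near-zero baseline it still gives improving patients the wrong sign and creates extreme values, which robust errors and the bootstrap leave in place. That needs a post-minus-pre difference, or the post measure adjusted for baseline.

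The cost is two sentences in the Aim 2 analysis text and the re-checking of a few flagged values against source. No extra data collection is needed.

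### The Aim 2 rejection sentence attaches the null's own conclusion to rejecting the null, so a significant predictor would be reported as not contributing, and the test for each predictor is not identified

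*Protocol*

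**What the plan says.** The text is in the protocol, section D (Research Design and Methods), under Specific to Aim 2.

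The outcome is the percent change in the Rasch FMA-UE from pre- to post-intervention. The predictors are the percent changes in trunk movement, voluntary elbow extension and a biceps-triceps co-contraction index, with the expectation that they matter: "We hypothesize that 3 independent variables will explain changes in UE motor impairment expected to occur with rehabilitation". The analysis is set up as follows: "Two multiple regression models will examine the relationships between the dependent and independent variables". One model pools the targeted patients and the other pools the non-targeted patients. All predictors are forced into each model, and a polynomial relationship is described as likely.

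The inference paragraph that closes the Aim 2 data analysis names the test statistic: "We will test significance of the coefficient of determination (adjusted R-square value) for each response variable". It then gives the null: "The null hypothesis tested is that there is no significant association between each response variable and the dependent variable". The plan explains this null as the variable making no contribution to motor ability. The opposing hypothesis is worded this way: "The alternative hypothesis is that the association is significant meaning that the response variable is associated with UE motor ability (FMA-UE person measure)". Last comes the rule, which is to reject the null when p is below 0.05, "which will lead to the conclusion that the response variable does not contribute to the FMA-UE score at a 0.05 significance level". Nothing is said about what to conclude when p is 0.05 or larger.

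**The concern.** Rejecting a null of no association is evidence for an association. The plan attaches the opposite statement to it. This is the only decision rule written for Aim 2, and Aim 2 is the part of the trial meant to show which movement and muscle-activity changes go with response, so that treatments can be refined. An analyst or reader who takes the sentence at its word would dismiss the predictors with the strongest evidence.

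There is a second weakness beside it. Adjusted R-square belongs to a fitted model, not to one predictor within it. Even with the rejection sentence put right, the plan would not say which p-value decides whether trunk movement, elbow extension or co-contraction is declared associated with the outcome.

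**Working it through.** The documents give no sample size, power or expected effect for Aim 2, so there is no figure to reproduce. The check is mainly one of logic.

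**1. The statements side by side (protocol, Specific to Aim 2).**

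| Element | Content |
|---|---|
| Null | No association; the variable does not contribute |
| Alternative | The variable is associated with the outcome |
| Rule | Reject the null if p < 0.05 |
| Conclusion on rejection | The variable does not contribute |
| Conclusion if p ≥ 0.05 | Not stated |

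The fourth row has the content of the first. Rejection should lead to the second. No reading makes the rows consistent.

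**2. Whether other text corrects it.** The SAP carries the same version number and date as the protocol, but deals only with Aim 1 and missing data. The protocol's Aim 2 hypothesis and its list of independent variables both expect association. They show what was meant, but neither is a decision rule.

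**3. How many decisions the rule governs.** 3 predictors × 2 models = 6, counting one decision per predictor. The wrong label attaches only to those of the 6 with p < 0.05.

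**4. What literal use would do (illustration, with assumed inputs).** The protocol's sample size paragraph gives 18 completers per group. Each arm has 3 impairment levels, so 18 × 3 = 54 per model if completion is equal and all neuromechanical data are present. Data were simulated as y = r·x₁ + √(1 − r²)·e, with x₁, x₂, x₃ and e independent standard normal. All three predictors were entered. The coefficient of x₁ was tested two-sided at 0.05 on 54 − 4 = 50 degrees of freedom, with 5,000 runs per value of r. The Monte Carlo standard error is at most √(0.25/5000) ≈ 0.007.

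| Assumed correlation r | Probability of the label "does not contribute" under the literal rule |
|---|---|
| 0 | 0.047 |
| 0.3 | 0.599 |
| 0.4 | 0.843 |
| 0.5 | 0.976 |

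The label goes to about 5% of predictors with no association and to 60–98% of those with the assumed associations. The values of r are not from the documents. The ordering does not depend on them, because the label is applied exactly when the test rejects.

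**5. The test statistic.** For a model with k terms, adjusted R² = 1 − (1 − R²)(n − 1)/(n − k − 1), which gives one value per model. The stated test for each variable could therefore mean any of the following:

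- the overall F-test, which gives the same p-value for all three predictors;
- three single-predictor regressions;
- a partial test within the full model.

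These can disagree when predictors are correlated. Correlation is plausible here, since the protocol's background (2f) describes trunk flexion as a substitute for elbow extension in reaching. With forced entry and one term per predictor, the natural per-predictor test is the increment in R²:

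F = (R²_full − R²_without j) / [(1 − R²_full)/(n − 4)] = t_j².

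This is the ordinary partial t-test. If a predictor enters with both a linear and a quadratic term, its contribution is tested jointly on 2 numerator degrees of freedom:

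F = [(R²_full − R²_without both)/2] / [(1 − R²_full)/(n − k − 1)].

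**The case against.** The strongest reply is that this is a stray negative. The null and alternative are given in the right direction immediately beforehand, the Aim 2 hypothesis and the list of predictors point the same way, and the same section says that all variables are expected to be associated with the FMA-UE measure. A competent analyst would read past the slip. The plan also commits to p-values, 95% confidence intervals and adjusted R-square, none of which depends on the faulty clause, so readers of the results would see any association for themselves. All of this stands and limits the practical consequence. It does not make the sentence correct, and a prespecified rule should not rely on being overridden.

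A reader might go further and infer that every Aim 2 conclusion would be reversed. The documents do not support that. Only the rejection case is worded. A predictor with p ≥ 0.05 is given no conclusion at all, which is a gap and not a reversal.

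A reader might also infer that an R-square criterion can never be applied to a single predictor. That is too strong, because the increment in R² can be tested and is equivalent to the partial t- or F-test. The fair criticism is that the plan names adjusted R-square without saying that such an increment is meant.

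**Conclusion.** The Aim 2 rejection sentence is wrong as written. It draws the null's conclusion from rejecting the null, against the hypotheses in its own paragraph, and no other text in the protocol or SAP corrects it. Under literal use, every rejection among the 6 predictor-level decisions would carry the wrong conclusion. If nothing is rejected, no wrong statement is made. The count of 6 assumes one decision per predictor. The illustrative probabilities rest on 54 patients per model, independent predictors and assumed correlations, and serve only to show the direction.

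The reference to adjusted R-square leaves the per-predictor test unidentified, and that would remain after the stray negative is removed. Estimates, p-values, confidence intervals, data collection, sample size and Aim 1 are untouched. This is an error of wording in an operative rule, probably a drafting slip, and it should be corrected before the Aim 2 analysis is run.

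**What to change.** Replace the test and decision sentences of the Aim 2 data analysis with:

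> For each predictor we test its partial contribution in the forced-entry model (two-sided t-test of the coefficient, or a joint partial F-test when both linear and quadratic terms are included). If p < 0.05 we conclude that the predictor is associated with the percent change in the Rasch FMA-UE; otherwise an association has not been shown.

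Report adjusted R-square once per model as a descriptive measure. In the same edit, call the three neuromechanical variables predictors instead of response variables, and name the outcome as percent change in the Rasch FMA-UE throughout, to match the Aim 2 dependent-variable paragraph. The joint test matters because the protocol itself expects polynomial relationships, and a t-test on one coefficient does not test a predictor that is represented by two terms.

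The cost is a few sentences in the protocol, or in an Aim 2 section added to the SAP. The 0.05 level, the design, the sample size and the data to be collected do not change.
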